Clinical Trial Protocol

Title:	An Exploratory Single Blind Study of Ergoloid Mesylates, 5-Hydroxytryptophan, and the Combination in Adult Males with Fragile X Syndrome
Substance Identifier:	Ergoloid mesylates, 5-hydroxytryptophan
IND Number:	Exempt
Indication:	Behavior, functional skills, cognition
Phase:	Phase 2
Sponsor:	[name], PhD – Study Sponsor Purposeful IKE (Funding Study Drug) FRAXA Research Foundation (Funding Study only)
Principal Investigator:	[name] MD PhD [name]
Protocol Version:	ERG/5-HTP in FXS Date: 23 May 2022 V4.0

SYNOPSIS	
Name of Sponsor/Company:	[name], PhD – Study Sponsor
	Purposeful IKE (Funding Study Drug)
	FRAXA Research Foundation (Funding Study only)
Name of Investigational Product:	Ergoloid mesylates, 5-Hydroxytryptophan
Study Title:	An Exploratory Single Blind Study of Ergoloid Mesylates, 5-
	Hydroxytryptophan, and the Combination in Adult Males with
	Fragile X Syndrome
Study Phase:	Phase 2

Study Objectives:

In male Fragile X participants aged 18-45 years, inclusive, receiving standard medications:

- To obtain preliminary assessments of the efficacy of Ergoloid Mesylates, 5-Hydroxytryptophan, and the Combination
- To evaluate the safety and tolerability of Ergoloid Mesylates, 5-Hydroxytryptophan, and the Combination
- To obtain biomarker (ERP and eye tracking) data on Ergoloid Mesylates, 5-Hydroxytryptophan, and the Combination

Exploratory Efficacy Outcome Measures

- NIH Toolbox Cognitive Battery for Intellectual Disabilities (NIH-TCB)
- KiTAP executive battery alertness, distractibility, go-nogo and flexibility subtests
- Clinical Global Impression Severity Investigator rated (CGI-S)
- Clinical Global Impression Improvement Investigator rated (CGI-I)
- Visual Analog Scale (VAS) rating for function, language and behavior using participant-specific anchors
- Aberrant Behavior Checklist (ABC)
- Anxiety, Depression, and Mood Scale (ADAMS)
- Vineland-3 Adaptive Behavior Scale
- Event-Related Potentials (ERP)
- Eye Tracking

Safety and Tolerability Endpoints

- Treatment-emergent Adverse events
- Changes in vital signs
- Clinical laboratory values for hematology and chemistry

Study Design

This is a single-center, Phase 2, single-blind, 4-period sequential study will obtain a preliminary assessment of the effects of ergoloid mesylates (EM) 1 mg TID and 5-hydroxytryptophan (5-HTP) 100 mg TID and the combination compared to a placebo period in participants with Fragile X Syndrome. The study will consist of a Screening period of up to 28 days prior to initial study drug administration, followed by four 4 week single-blind treatment periods. The screening and baseline visits may occur at the same time, provided the results of safety labs can be obtained. A final follow-up visit or phone contact for safety is planned one week after the conclusion of Period 4.

Eligible participants will be started on EM for 4 weeks in Period 1, then will take EM and 5-HTP for 4 weeks in Period 2, then, 5-HTP for 4 weeks in Period 3, then placebo for 4 weeks in Period 4. Study visits will occur at baseline and every 4 weeks at transition times between periods, then at the end of the study.

Brief cognitive and behavioral assessments will be performed during each clinic visit. Safety and tolerability assessments will include adverse event monitoring, vital signs, blood chemistry and hematology, and urinalysis.

	4 Weeks Period 1	4 Weeks Period 2	4 Weeks Period 3	4 Weeks Period 4		
Screen/Enroll ───→	EM	EM + 5-HTP	5-HTP	Placebo		
N=15 participants						
EM=ergoloid mesylates 1 mg TID, 5-HTP = 5-hydroxytryptophan 100 mg TID						
Planned Numbers of Participants						
Enrollment of a total of 15 eligible participants is planned.						
Study Duration						
The total duration of the study for each participant will be up to 21 weeks, including a maximum of 4-week screening						

The total duration of the study for each participant will be up to 21 weeks, including a maximum of 4-week screening period, four 4-week Single-Blind treatment Periods, and a follow-up telephone call approximately 1 week after the last treatment visit.

Study Procedures:

The Screening Visit will occur up to 28 days prior to the first study drug administration on Day 1. During screening, participants and their parent/legal authorized guardian, if indicated, will review and sign an Informed Consent/Assent form prior to any study procedures being performed. Following confirmation of a prior diagnosis for Fragile X, participants will have information collected regarding their neurological and medical/surgical history, race/ethnicity, social history (tobacco, alcohol, and/or drug use), and use of prescription and over-the-counter medications. Participants will undergo a full physical exam, and have vital signs measured. Height, weight, and BMI will also be collected. Fasting blood samples will be collected for chemistry and hematology. Urine will be collected for urinalysis. The Stanford-Binet version 5 will also be administered at screening, as will an assessment of suicidality risk.

At the Baseline visit (Period 1/Day 1), participants will receive an abbreviated physical examination including vital signs. However, these will not be repeated if the Screening and Baseline visits occur on the same day. Cognitive, behavioral, ERP and eye tracking assessments will be performed, and these measurements will be used as a common set of baseline measurements to which post-treatment assessments will be compared for all treatment Periods.

During all four single-blind periods, participants will receive three times a day treatment with single-blinded study medication, two caps three times a day, each dose at least 4 hours apart. In the first period they will take an EM capsules and a placebo capsule at each dose, the second period an EM and 5-HTP caps at each dose, the third period a 5-HTP and placebo capsule each dose, and the fourth period 2 placebo capsules each dose. EM and 5-HTP will be over-encapsulated to maintain the single-blind.

Participants will return to the clinic at the end of each Period at weeks 4, 8, 12, and 16. Cognitive and behavioral evaluations will be repeated at Weeks 4, 8, 12, and 16 (end of Period 1, 2, 3, 4). Additionally, participants will be monitored for adverse events via a telephone call at the end of Week 1 of each Period, and one week following completion of Period 4 or following early discontinuation. During clinic visits, adverse effects will be assessed, and laboratory measures and vital signs will be repeated according to the Schedule of Assessments. Suicidality risk will also be evaluated during the treatment periods per the Schedule of Assessments; if a concern is detected, the participant will be referred for further evaluation and treatment.

Participant Inclusion/Exclusion Criteria:

Individuals are eligible for the study if they meet all of the Inclusion and none of the Exclusion criteria. The criteria below will be assessed during Screening, which will be up to 28 days prior to first study drug administration. Continued participant eligibility will be verified on Baseline Day 1.

Participant Inclusion Criteria

- 1. Male aged 18 to 45 years, inclusive.
- 2. Participant has Fragile X Syndrome with a molecular genetic confirmation of the full Fragile X Mental Retardation (FMR1) mutation (≥200 CGG repeats).
- 3. Current treatment with no more than 3 prescribed psychotropic medications. Anti-epileptic medications are permitted and are not counted as psychotropic medications if they are used for treatment of seizures. Anti-epileptics for other indications, such as the treatment of mood disorders, count towards the limit of permitted medications.
- 4. Permitted concomitant psychotropic medications must be at a stable dose and dosing regimen for at least 2 weeks prior to Screening and must remain stable during the period between Screening and the commencement of study medication.
- 5. Anti-epileptic medications must be at a stable dose and dosing regimen for 12 weeks prior to Screening and must remain stable during the period between Screening and the commencement of study medication.
- 6. Participants with a history of seizure disorder who are currently receiving treatment with anti-epileptics must have been seizure-free for 3 months preceding screening, or must be seizure-free for 3 years if not currently receiving anti-epileptics.

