- 5. Significant hearing or visual impairment that may affect the participant's ability to complete the test procedures.
- 6. Concurrent major psychiatric condition (e.g., Major Depressive Disorder, Schizophrenia or Bipolar Disorder) as diagnosed by the investigator. Participants with additional diagnosis of Autism Spectrum Disorder or Anxiety Disorder will be allowed as these are characteristics of FXS.

- 7. Participant has active diseases that would interfere with participation, such as acquired immunodeficiency disorder, hepatitis C, hepatitis B, or tuberculosis.
- 8. Participant is planning to commence psychotherapy or cognitive behavior therapy (CBT) during the period of the study or had begun psychotherapy or CBT within 4 weeks prior to Screening.
- 9. Participant has participated in another clinical trial within the 30 days preceding Screening.

Investigational Product, Dosage, and Mode of Administration:

In this single-blind, 4-period study, 15 participants will be enrolled and will be treated with the following during the 4 periods of the study.

- Ergoloid mesylates 1 mg TID (Medisca)* and matching placebo for 5-Hydroxytrptophan 100mg TID***
- Ergoloid mesylates 1 mg TID (Medisca) and 5-Hydroxytryptophan 100 mg TID (5-HTP, Basic Vitamins)**
- 5-Hydroxytryptophan 100 mg TID (5-HTP, Basic Vitamins) and matching placebo for Ergoloid mesylates 1mg TID***
- Matching placebo for Ergoloid mesylates 1mg TID and Matching placebo for 5-Hydroxytryptophan 100mg TID***
- •

* 1 mg will be mixed with methyl cellulose and placed in a size 00 capsule

** will be over-encapsulated in identical size 00 capsules

***will be ascorbic acid powder in identical size 00 capsules

All study medications will be prepared at the Rush Oak Park Compounding Pharmacy and provided to the RUMC Investigational Pharmacy for dispensing as identical-appearing capsules in bottles. Two bottles of capsules will be provided at each visit and one capsule from each bottle will be taken 3 times a day. Doses should be taken at least 4 hours apart.

Overview of Endpoints

Exploratory Efficacy Outcome Measures

- NIH-TCB: Cognitive battery assessing different domains of cognition, administered using an iPad
- KiTAP: Computerized executive battery with assessments of alertness (reaction time), distractibility, go/nogo (impulsiveness), and flexibility
- Clinical Global Impression Severity Investigator rated (CGI-S) Standardized ranking scale with 7 rankings

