4 INVESTIGATIONAL PLAN

4.1 Overall Study Design

This is a single center, Phase 2, single-blind, 4 period study to obtain preliminary assessment of the effects of ergoloid mesylates (EM), 5-hydroxytryptophan (5-HTP), and the combination in participants with Fragile X Syndrome. As schematic display of the study design is shown in Figure 7.

The study will consist of a Screening period of up to 28 days prior to initial study drug administration, followed by four 4-week single-blind treatment periods. The screening and baseline visits may occur at the same time, provided the results of safety labs can be obtained. No washout period will be utilized between treatment periods. A final follow-up phone contact for safety is planned one week after the conclusion of Period 4.

Eligible participants will be started on over-encapsulated EM 1 mg TID during Period 1, then will take EM 1 mg TID and 5-HTP 100 mg TID in Period 2, then 5-HTP 100 mg TID in Period 3, and placebo in Period 4. Throughout all 4 periods, participants will take two identical capsules three times a day. If only taking one over-encapsulated drug, they will take one over-encapsulated placebo pill with the drug at each dose, and when in period 4 they will take two over-encapsulated placebo pills at each dose.

Cognitive and behavioral assessments will be performed during each clinic visit. Safety and tolerability assessments throughout the study will include adverse event monitoring, vital signs, blood chemistry, hematology, and urinalysis.

Figure 7 Study Design Schematic

N=15 participants

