6.4 Blinding

This is a single-blind study, meaning the participant and his family/caregivers will not know what drug or combination the participant is receiving. The investigator and study coordinator will know what drug the participant is taking. The remainder of the study team performing assessments such as the Vineland, eye tracking, ERP, Toolbox, and the KiTAP will not know the type of treatment the patient is on when testing is done.

The PI or designee will be responsible for maintaining the single blind, consistent with protocol design, throughout the study, except in the case of an emergency need to unblind the participant for medical reasons. Blinding is not to be broken during the study unless considered necessary by the Investigator for emergency situations for reasons of participant safety. When the blind is broken, the reason must be fully documented.

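### One fixed treatment order without washout aliases treatment with period: the announced placebo comparison and the changes from baseline need assumptions the plan does not state, and nothing masks the offline ERP and eye-tracking reads for visit

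*Combined protocol and SAP*

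**What the plan says.** **Order and washout.** The Synopsis (Study Design, Study Procedures) and Section 4.1 give every participant the same sequence: EM, then EM + 5-HTP, "then, 5-HTP for 4 weeks in Period 3, then placebo for 4 weeks in Period 4". Section 4.1 adds: "No washout period will be utilized between treatment periods".

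**Comparisons.** The Synopsis says the study will assess EM, 5-HTP and "the combination compared to a placebo period in participants with Fragile X Syndrome". Its Study Procedures make the Day 1 assessments "a common set of baseline measurements to which post-treatment assessments will be compared for all treatment Periods". Section 10.4 plans descriptive statistics at each time point and, for cognitive parameters, change from baseline. It contains no active-minus-placebo contrast, no model, and no assumption about time, practice, expectancy or carry-over.

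**Blinding.** Under Section 6.4, the staff who perform assessments such as the Vineland, eye tracking, ERP, Toolbox and KiTAP "will not know the type of treatment the patient is on when testing is done". The same section says: "The PI or designee will be responsible for maintaining the single blind, consistent with protocol design". It also says: "The investigator and study coordinator will know what drug the participant is taking". Section 7.11.1.8 assigns the EEG reading to a named reader, and Section 7.11.1.9 has eye tracking analysed offline by a specialist. Neither says that the reads are masked for visit or period.

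**The concern.** Each treatment occurs in exactly one period, so a difference between treatments is also a difference between visits 4 to 12 weeks apart. The full battery is given five times (Section 7.11.2), so practice on the cognitive tasks is a realistic source of drift. Placebo comes last. A steady gain therefore works against the active treatments when they are set against placebo, and in favour of the later periods when they are set against baseline. The two comparisons that the Synopsis describes can be biased in opposite directions, and no section warns the reader.

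The fixed order also bears on blinding. In a study with varied orders, knowing the visit does not disclose the treatment. Here it does, for anyone who knows the sequence, and the ERP and eye-tracking files are scored away from the test session.

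**Working it through.** The plan has no figure to reproduce: Section 10.1 gives no calculation, effect size or SD. The check is whether the contrasts can be identified.

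**Inputs.** There are 15 participants and one sequence (Synopsis), with five occasions: baseline and Weeks 4, 8, 12 and 16 (Section 7.11.2). Complete data are assumed, although Section 5.5 does not replace withdrawals. Every model includes participant effects. Standard errors (SE) are in units of the within-participant residual SD.

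**1. Free time effects.**
- Four treatment periods: 15 + 3 = 18 independent columns before treatment is added. Adding three treatment columns gives 21 columns, but the rank stays 18. Estimable: 0 of 3.
- Baseline added (five occasions): 15 + 4 = 19 before treatment. With treatment there are 22 columns and the rank is still 19. Estimable: 0 of 3.

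**2. No time effect, no carry-over, placebo response allowed.** Rank 19 of 19; estimable 3 of 3. Each contrast is a difference between two visits, with SE = √(2/15) = 0.365.

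**3. Linear time, no carry-over, no placebo response.** Rank 19 of 19; estimable 3 of 3. The slope is then (placebo mean − baseline mean)/4, so the whole time correction rests on placebo doing nothing.
- EM: ȳ₁ − ¾ȳ₀ − ¼ȳ₄, SE = √[(1 + 0.5625 + 0.0625)/15] = 0.329
- EM + 5-HTP: ȳ₂ − ½ȳ₀ − ½ȳ₄, SE = √[(1 + 0.25 + 0.25)/15] = 0.316
- 5-HTP: ȳ₃ − ¼ȳ₀ − ¾ȳ₄, SE = 0.329

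**4. One further term.** Adding to model 3 a quadratic time term, a placebo response, or a carry-over from Period 3 to Period 4 gives rank 19 of 20 in each case. Estimable: 0 of 3.

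**5. Size of a time effect.** Let scores improve by g at each visit, giving occasion shifts of 0, g, 2g, 3g and 4g.

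| | EM | EM + 5-HTP | 5-HTP | Placebo |
|---|---|---|---|---|
| Active minus placebo | g − 4g = −3g | −2g | −1g | – |
| Change from baseline | +1g | +2g | +3g | +4g |

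The documents give no g. For an assumed range of 0.05 to 0.20 SD:
- EM minus placebo shifts by −0.15 to −0.60 SD, which is 0.15/0.365 = 0.41 to 0.60/0.365 = 1.64 SE.
- The placebo-period change from baseline shifts by +0.20 to +0.80 SD, which is 0.55 to 2.19 SE.

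A constant expectancy effect e in all four periods cancels from active minus placebo but adds e to every change from baseline.

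**6. Carry-over.** Period 1 follows no study drug, so it cannot contain any. Later outcomes are taken at the end of four-week periods, so an effect must last about four weeks to matter. The direction depends on the model. Suppose a fraction c carries over and single-agent effects equal t. The shifts in the three contrasts (EM, EM + 5-HTP, 5-HTP) are:
- −ct, 0, 0 if the whole preceding effect carries over and the combination also equals t;
- −ct, −ct, 0 if only a stopped drug carries over;
- −ct, 0, +ct if the whole preceding effect carries over and the combination is additive (2t).

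No single carry-over figure is justified.

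**7. Masking.** Section 6.4 speaks of the moment of testing. The schedule in Section 14.1 labels each visit by period, and the Synopsis and Section 4.1 print the order. No section withholds the order from assessors or removes the visit label before offline scoring.

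**The case against.** The study is openly exploratory, sequential and descriptive, with no sample-size calculation. A single-sequence pilot is a legitimate choice. Section 10.4 plans no placebo contrast, and Section 4.1 does not repeat the Synopsis phrase that announces one, so the models above are ones nobody proposes to fit. The bias sizes come entirely from an assumed steady g. Carry-over would have to persist for about four weeks. Section 6.4 already requires that the listed assessors not know the treatment and makes someone responsible, which under a fixed order implies keeping the order from them. The remedy does not make any contrast estimable.

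Most of this stands and limits the consequence to interpretation. But an exploratory label does not tell a reader that treatment and period cannot be separated, and the Synopsis still announces a comparison with placebo.

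A reader might infer three stronger points that the documents do not support:
- *Assessors will be unblinded.* A safeguard is missing, but nothing shows that assessors will know the order or that the files carry visit labels. The Vineland informant is a caregiver, and caregivers are blinded.
- *The CGI contradicts the blinding.* The Synopsis lists "Clinical Global Impression Severity Investigator rated (CGI-S) Standardized ranking scale with 7 rankings", and the CGI-I is likewise investigator rated. Section 6.4 says openly that the investigator knows the drug, so the unblinded status is disclosed.
- *Order was meant to be randomized.* References to randomization appear in the Synopsis and in Sections 5.3, 7.2, 7.11.2.1 and 10.3, but no randomization is described. The point is editorial.

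**Conclusion.** The concern holds as a limit on interpretation and should be fixed. Without restrictions on time, 0 of 3 active-minus-placebo contrasts are estimable. It would go too far to say they can never be identified: all 3 are under the assumptions in steps 2 and 3, but the plan states none of these and its data cannot test them against a free period effect. Changes from baseline have the same weakness through time, practice and expectancy, and after Period 1 through carry-over.

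Time and practice are the stronger part. Carry-over is secondary and has no fixed direction. The ranks and standard errors assume complete data and a common residual SD. The size of any shift rests on an assumed g.

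On blinding, the supported conclusion is narrow: with one fixed order, the stated rater blinding is not backed by any step that masks the offline ERP and eye-tracking reads.

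**What to change.** 1. **Mask the offline reads.** Strip visit label, period number and date from the ERP and eye-tracking files. Have the existing readers score each participant's sessions in random order after that participant's last visit. Cost: relabelling at most 15 × 5 = 75 sessions of each type, and holding the reads until Week 16 or withdrawal.

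2. **State the limitation in Section 10.** For example: *Because all participants receive the treatments in one order without washout, differences against placebo and between treatments, and changes from baseline, cannot be separated from time, practice or expectancy (or, after Period 1, from carry-over) without further assumptions. Results will be reported as changes by period, and conclusions limited accordingly.* Align the placebo-comparison wording in the Synopsis with this. Cost: a short addition to the text and a more modest stated conclusion.

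Minor clarifications:
- In Section 6.4, say that the order is withheld from the listed assessors. They would need instructions that omit the sections printing it.
- In Section 6.4, note that the investigator-rated CGI-S and CGI-I are unblinded.
- Reconcile the references to randomization with the non-randomized design.

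Treatments, visits, capsules and sample size are unchanged.

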- Clinical Global Impression Improvement Investigator rated (CGI-I): Standardized ranking scale with 7 rankings
- Visual Analog Scale (VAS) Parent/caregiver-rated assessment of participant-specific behavioral anchors: Domains of daily functioning, anxiety/irritability and language.
- ABC: Parent/caregiver-rated scale with six subscales to assess irritability, social avoidance, lethargy, hyperactivity, inappropriate speech and social avoidance, using ABC-FX factoring system.
- ADAMS: Parent/caregiver rated scale with a total score and five sub-scores to assess manic/hyperactive behavior, depressed mood, social avoidance, general anxiety, and obsessive/compulsive behavior.
- Vineland-3 Adaptive Behavior Scale: Clinician-administered standardized interview yielding adaptive behavior composite score and domain standard scores in domains of: communication (receptive, expressive, and written adaptive language functions), daily living skills (personal, domestic, and community skills), socialization (interpersonal relationships, play and leisure time, and coping abilities), and motor skills (gross and fine motor skills).
- Event-Related Potentials (ERP) Measure of auditory habituation based on EEG signals
- Eye Tracking Measure of gaze aversion (social anxiety) and pupilometry (autonomic function)

Safety and Tolerability: The safety variables to be assessed include adverse events; clinical laboratory parameters (chemistry, hematology, and urinalysis); physical examinations; and vital signs (including blood pressure, heart rate, and respiratory rate).

Statistical Considerations

Efficacy Analyses

The primary efficacy population will be the intent to treat (ITT) efficacy population, which will include all participants who received at least one dose of treatment and returned for at least one follow-up visit. The completers population (CP), defined as all randomized participants who complete all 4 treatment periods with no significant protocol violations, will be used to evaluate the robustness of the ITT results.

All efficacy parameters will be summarized at each time point collected and standard descriptive statistics provided. Baseline measurements are defined as those obtained on Day 1/Period 1 prior to receipt of any study medication. For cognitive parameters measured at baseline, change from baseline will also be calculated and standard descriptive statistics provided for each time point.

Safety Analyses

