10.4 Efficacy: Cognitive, Behavioral and Pharmocodynamic Measures Analysis

All cognitive and behavioral parameters will be summarized at each time point collected and standard descriptive statistics provided. Baseline measurements are defined as those obtained on Day 1/Period 1 prior to receipt of any study medication. For cognitive parameters measured at baseline, change from baseline will also be calculated and standard descriptive statistics provided for each time point.

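### The Synopsis promises a comparison with the placebo period, but the only planned contrast is change from Day 1, which in this fixed order carries 4, 8 and 12 weeks of drift

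*Combined protocol and SAP*

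**What the plan says.** - **Aim.** Synopsis, Study Design: the study is a preliminary assessment of EM, 5-HTP and "the combination compared to a placebo period in participants with Fragile X Syndrome". Section 4.1 restates the aim without naming placebo as comparator.
- **Order.** The same part of the Synopsis: "Eligible participants will be started on EM for 4 weeks in Period 1, then will take EM and 5-HTP for 4 weeks in Period 2", followed by 5-HTP alone and finally placebo. There is one group and one order.
- **Reference.** Synopsis, Study Procedures, on the Day 1 cognitive, behavioral, ERP and eye-tracking assessments: "these measurements will be used as a common set of baseline measurements to which post-treatment assessments will be compared for all treatment Periods".
- **Analysis.** Section 10.4, and the Synopsis under Efficacy Analyses: "Baseline measurements are defined as those obtained on Day 1/Period 1 prior to receipt of any study medication". The one contrast follows: "For cognitive parameters measured at baseline, change from baseline will also be calculated and standard descriptive statistics provided for each time point".
- **Data available.** Sections 7.11.2.2 and 14.1 schedule the full battery at the end of every period, including placebo at Week 16. Its values will appear in the per-visit summaries, but no text takes a difference from them.

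**The concern.** The Synopsis names a comparison that the analysis text never carries out. The comparison it does carry out has a weakness specific to this design. Regimen and time are completely tied together, so a change from Day 1 contains the regimen effect plus everything else that moved since Day 1. The same participant repeats NIH-TCB and KiTAP at five visits, and the same caregiver repeats ABC, ADAMS and VAS. Practice or a trend in ratings would favour whichever regimen comes later, and the combination and 5-HTP alone would look better than EM without any drug effect. Day 1 and Week 16 bracket the three active visits, so the trial already collects what is needed to show how far the results depend on the reference.

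**Working it through.** The plan states no SD, correlation, dropout rate, alpha or power (Section 10.1 declines a sample size calculation), so there is no figure of its own to reproduce.

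**Inputs from the documents.** Visits at Weeks 0, 4, 8, 12 and 16; 15 participants (Synopsis); no washout (Section 4.1); no replacement of withdrawals (Section 5.5); visit windows of ±5, read as days (Section 14.1).

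**Assumed model.** Score = participant effect + drift m(t) + regimen effect + visit error with SD s. Scores are oriented so that higher is better. The participant effect cancels in every contrast below.

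**Contrasts at t = 4, 8, 12.**
- (a) Yt − Y0
- (b) Yt − Y16
- (c) Yt − [(1−w)Y0 + wY16], with w = t/16 = 0.25, 0.50, 0.75

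A mean model with intercept, linear time and three regimen effects gives exactly the weights in (c). It has five parameters for five visit means, so it is saturated and the data cannot test linearity.

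**Bias at Weeks 4 / 8 / 12.**

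| Non-drug change | (a) | (b) | (c) |
|---|---|---|---|
| Linear, 0.2s per visit | +0.2s / +0.4s / +0.6s | −0.6s / −0.4s / −0.2s | 0 / 0 / 0 |
| Step of 0.4s after first test | +0.4s / +0.4s / +0.4s | 0 / 0 / 0 | +0.3s / +0.2s / +0.1s |
| Saturating, 1−exp(−k) at visit k | +0.63 / +0.86 / +0.95 | −0.35 / −0.12 / −0.03 | +0.39 / +0.37 / +0.21 |
| Shift p at Week 16 only | 0 / 0 / 0 | −p / −p / −p | −0.25p / −0.50p / −0.75p |

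No contrast is best in every row.

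**Variance with equal variances and equal correlation.** (a) and (b): 2s². (c): s²[1 + (1−w)² + w²].
- Weeks 4 and 12: 1 + 0.5625 + 0.0625 = 1.625, which is 18.75% below 2.
- Week 8: 1 + 0.25 + 0.25 = 1.5, which is 25% below 2.
- 95% half-width with 15 participants, 2.145 × √(variance/15): 0.78s for (a); 0.71s, 0.68s and 0.71s for (c).

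**How far that gain depends on assumptions.**
- AR(1) errors with four-week correlation 0.3 to 0.7: reductions of 16–18%, 27–37% and 40–62% at Weeks 4, 8 and 12.
- Week 16 error variance doubled: Week 4, 1.6875 (15.6% lower); Week 8, 1.75 (12.5% lower); Week 12, 1 + 0.0625 + 2 × 0.5625 = 2.1875 (9.4% higher).
- Week 16 missing for some who still contribute to (a): with 12 available, (1.625/12)/(2/15) = 1.016 at Weeks 4 and 12; with 11 available, (1.5/11)/(2/15) = 1.023 at Week 8. The gain is therefore gone with three and four missing visits respectively.

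**Windows.** If nominal weights are used, the residual drift is at most 5 + 5w days: 6.25, 7.5 and 8.75 days. Weights from actual days remove this.

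**The case against.** The strongest reply is that nothing here is an error. The study is exploratory and descriptive, no test or claim rests on change from Day 1, and the Week 16 summaries sit next to the others for anyone to compare. The first two parts stand: this is an improvement to reporting, and it does not show the planned summaries to be invalid. The third does not fully answer the point. Per-visit means and SDs do not give the SD or interval of a within-participant difference, and the Synopsis names the placebo comparison as part of the aim.

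The second reply is that the time-weighted contrast is only one estimator and not always the better one. This also stands. For a step after the first test, and for the fast-saturating drift in the table, the plain Week 16 difference is less biased. Day 1 precedes any capsule while Week 16 is on placebo, so contrast (c) keeps 75% of an expectancy step at the EM visit.

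A reader might infer three stronger things that the documents do not support:
- **That (c) should replace change from Day 1.** The saturated model makes its key assumption untestable.
- **That a 19–25% variance reduction is a property of this trial.** The documents give no variance, correlation or dropout rate, and withdrawals are not replaced.
- **That errors from using Week 16 are always conservative.** That is true only of persisting benefit. Under Section 6.4 the investigator knows the treatment, and CGI-S is investigator rated. A less favourable rating in the known placebo period, or worsening after 5-HTP stops, would inflate all three regimen estimates in (b) and (c).

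**Conclusion.** The point holds as a gap between aim and analysis, with an inexpensive remedy. The placebo comparison in the Synopsis has no analysis behind it. The contrast that is planned carries 4, 8 and 12 weeks of drift at the EM, EM + 5-HTP and 5-HTP visits, and is limited in Section 10.4 to cognitive measures although the Study Procedures text covers all of them. The size of any drift is unknown.

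Contrast (c) removes linear drift exactly and reduces a step after the first test to 75%, 50% and 25% of its size; (b) removes such a step entirely. The 19%, 25% and 19% variance reductions of (c) over (a) require equal variances, equal between-visit correlation and complete Week 16 data. Contrasts (b) and (c) both require that no drug or withdrawal effect remains at Week 16 and that no rating shift is specific to placebo. Because each contrast fails in a different way, the value lies in showing all three. Agreement would be reassuring; disagreement would show that a regimen ranking depends on the reference.

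**What to change.** In Section 10.4 and the Synopsis efficacy text, state how the placebo comparison will be made. For every score measured at both Day 1 and Week 16 (so not CGI-I, which has no Day 1 value), report at each active visit, with n, mean, SD and 95% CI:

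- (a) change from Day 1;
- (b) difference from the Week 16 placebo visit;
- (c) Yt − [(1−w)Y0 + wY16], with w = actual days from Day 1 to visit t divided by actual days from Day 1 to Week 16 (nominally 0.25, 0.50, 0.75).

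Use only true end-of-placebo values as Y16. Section 9.3.5 has the Week 16 procedures done at early withdrawal, possibly on active drug, and those values must not enter.

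State the assumptions beside the table: (b) assumes no drift between visit t and Week 16; (c) assumes linear drift, which these data cannot test; both assume no remaining drug or withdrawal effect and no placebo-specific rating shift. Fix the formulas before the data are reviewed.

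The cost is a few lines of text and two further derived differences per score and active visit, with no new visits or tests. The downsides: participants without Week 16 contribute only to (a), persisting benefit shrinks (b) and (c), and worsening or less favourable rating on placebo inflates them.
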